### 3.4.4 Handling of missing data

For variables obtained only at the baseline visit, missing values will not be replaced.

For the self-reported satisfaction questionnaire items, collected at the end of study visit, missing values will not be replaced. For variables measured daily during the observation period such as sensor-generated data, CAT score, and labelling information, missing data will not be imputed for all descriptive statistical analyses performed. The CAT score and derived sensor variables may be imputed for the purpose of building machine learning models if needed to avoid loss of instances using a suitable imputation method (e.g., LOCF, Forward filling, multiple imputation [MI], recursive imputation, median imputation). Sensitivity analyses will be conducted to assess the impact of imputation.

For variables with values collected at baseline, at the exacerbation visit and at end of study visit, missing values will not be imputed for all descriptive statistical analyses. Lung function parameters and lab values may be imputed for the purpose of building machine learning models if needed to avoid loss of instances by LOCF method if the last (previous) available value is recorded within 2 weeks before the date of the visit of interest. In cases where no value for a variable is available for a participant, imputation strategies across instances may be used (e.g., median imputation or iterative imputation methods). Sensitivity analyses will be conducted to assess the impact of imputation.

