Covariates (status at the time of Day 0, closest record prior to):

- Demographics data at baseline: (sex, age, height, and weight, race and ethnicity)
- Body mass index will be calculated based on height and weight
- Smoking status (current, ex-, non-smoker)
- Medical history at baseline
 - Date of diagnosis of COPD
 - Number of moderate or severe exacerbations prior to baseline visit (preceding 36 months, in case available)
- Comorbidities at baseline
- Current medication including COPD treatment at baseline
- COPD severity (GOLD stage)

Lung Function and Laboratory variables

(at Day 0, moderate/severe exacerbation visit and End of study visit)

- Body plethysmography parameters: FEV1 [L], FVC [L], FEV1/FVC, TLC [L] (total lung capacity), RV [L] (residual volume), FRC_{pleth} [L] (functional reserve capacity), IC [L] (inspiratory capacity), R_{aw} [kPa s L⁻¹] (=ratio of sRaw to FRC_{pleth}; airway resistance), sR_{aw} [kPa s] (specific airway resistance), VT [L] (mean tidal volume), ERV [L] (expiratory reserve volume), IRV [L] (inspiratory reserve volume). For definitions see [Criée 2011](#).
- Blood gas analysis:(capillary) pO₂ [mmHg], O₂ saturation [%] and pCO₂ [mmHg],
- Serum CRP [mg/l] and serum procalcitonin levels [ng/ml]
- Blood count (CBC with differential); only values that are available with routine blood counts: Hb [g/dL], Hct [%], Erythrocyte count [10⁶/μL], MCV [fL], MCH [pg], MCHC [g/dL], Reticulocytes [x10³/μL] [% (of erythrocytes)], RDW [], platelet count [10³/μL], WBC count [x10³/μL], Lymphocytes [x10³/μL] [%], Monocytes [x10³/μL] [%], Neutrophils [x10³/μL] [%], Eosinophils [x10³/μL] [%], Basophils [x10³/μL] [%]

Derived and transformed data needed for the analysis are described in Section [9.7.1.1](#).

A complete mapping of objectives, outcomes and variables is available in Section [14.1.2](#).

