#### 3.4.2 Considerations for potential confounders and effect modifiers

Not applicable. All available features will be considered in the predictive modelling.

For objective 4, smoking status, and other relevant baseline covariates will be forced into the models.

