Different machine learning algorithms will be evaluated, and their performance will be assessed by estimating their accuracy, specificity, sensitivity, and area under ROC metrics. Other usual evaluation metrics such as precision, positive predictive value (PPV), negative predictive value (NPV), F1-score will be computed.

This analysis will be performed on the COPD cohort. Internal cross-validation will be tested.

The following models will be used:

- Logistic regression
- Random Forest
- K-nearest neighbors
- Boosting methods (e.g., Gradient boosting machine, GBM)
- Support vector machines (SVM)

Other methods may be tested.

The development of those models will be based on the machine learning algorithms implementation of scikit-learn (12), a python package designed for predictive data analysis. Other packages may be considered if needed (e.g., H2O (13)).

To optimize the performance of the models, feature extraction and selection algorithms will be used.

Explanatory models will be built on top of the selected machine learning algorithm (14), as a way to support rationalization for physicians and regulatory organizations. Depending on the selected ML model selected, either model specific (for logistic regression, decision trees, k-nearest neighbors) or model agnostic methods will be considered (global methods as PDP, ALE, functional decomposition, and local methods as LIME and Shapley values).

### 3.4.5.3 Secondary Objective 3

Objective 3 will be analyzed on the COPD cohort. For each pair of variables and outcomes ( $x, y$ ) defined below, Pearson's correlation coefficient will be computed together with a 95% asymptotic confidence interval based on Fisher's Z transform.

In case of low variability in parameter values (e.g., exacerbation count), parameters may be treated as ordinal and analyzed in terms of Kendall's Tau statistic with non-parametric confidence interval (see (15)).

The following variable groups and outcomes will be paired and assessed at the indicated time points:

Group x	Group y	Time points for assessment
Sensor data (see section 2.1.4), daily averages (17 variables): physical activity, heart rate, resting heart rate, heart rate variability, temperature, respiration rate, ratio of in- vs expiration time, cough frequency, sleep pattern (hours of sleep)	CAT summary score: Self-assessed patient's health status by CAT questionnaire.	Baseline (Day 0), End of study visit

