#### **3.4.6 Sensitivity analyses**

To assess effect of missing values, sensitivity analyses will be performed to run models with variables with a missing rate less than or equal to 20% (17).

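### The rule that missing baseline-only covariates are not replaced has no exception for the machine learning models, so models needing complete rows must drop the covariate or lose the participant

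*SAP*

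**What the plan says.** SAP 3.4.4 opens its missing-data rules with "For variables obtained only at the baseline visit, missing values will not be replaced". Protocol 9.7.1.2 has the same sentence. Neither document limits it to a type of analysis.

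The other rules in SAP 3.4.4 are built differently. For daily variables, imputation is ruled out for descriptive analyses only, and then: "The CAT score and derived sensor variables may be imputed for the purpose of building machine learning models if needed to avoid loss of instances". For values taken at baseline, exacerbation and end-of-study visits, the pattern is the same: "Lung function parameters and lab values may be imputed for the purpose of building machine learning models if needed to avoid loss of instances". The paragraph on these repeated-visit variables goes on: "In cases where no value for a variable is available for a participant, imputation strategies across instances may be used", with median and iterative imputation as examples.

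Baseline-only variables are inputs to the prediction models. The mapping in protocol 14.1.2 lists them for Objectives 2 and 5: demographics, BMI, smoking status, medical history, date of diagnosis, prior exacerbations, comorbidities, medication and GOLD stage. SAP 3.4.2 says "All available features will be considered in the predictive modelling". Protocol 9.3 makes collection of all variables subject to availability and repeats the caution for one covariate: "Number of moderate or severe exacerbations prior to baseline visit (preceding 36 months, in case available".

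SAP 3.4.5.2 names logistic regression, random forest, k-nearest neighbours, boosting and support vector machines, and compares their performance.

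**The concern.** The plan recognises that a missing feature can cost data rows and provides for this in two classes of variable. It leaves out the third class, where a gap does the most damage. A baseline covariate is constant within a participant, so one unfilled value affects every event day and control day of that person, whereas a gap in a daily variable affects only the days concerned.

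Logistic regression, support vector machines and k-nearest neighbours, in their standard form, need a complete feature row. With no replacement allowed, the analyst must either leave out the covariate or leave out the participant, and the plan does not say which. The first choice could remove a clinically obvious predictor such as the prior exacerbation count. The second removes events from the primary model and favours participants with fuller charts. If some algorithms tolerate gaps and others do not, their sensitivity, specificity and area under the ROC curve could be estimated on different participants, which weakens the comparison between them.

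**Working it through.** **1. The text side by side (SAP 3.4.4)**

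| Class of variable | Descriptive analyses | Machine learning |
|---|---|---|
| Daily (CAT, sensor) | not imputed | CAT and derived sensor values may be imputed |
| Baseline, exacerbation and end-of-study visits | not imputed | lung function and laboratory values may be imputed |
| Baseline only | not replaced (no distinction made) | no exception stated |

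The across-instance sentence stands in the paragraph on the second class. Read by position, it does not reach baseline-only variables and the rule stands without exception. Read by its general wording, it allows what the opening sentence forbids. Either way the section needs correction.

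**2. The plan's own figures (SAP 1.3.2, protocol 9.5)**

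- Events needed: with true sensitivity 0.85, an exact one-sided 95% lower limit of at least 0.50 and assurance 0.95, the first qualifying sample is 18 events (at least 13 of 18 detected, assurance 0.958). This reproduces the plan's 18.
- Expected events: 60 participants × 0.5 events in 3 months = 30.
- Chance of enough events: P(X ≥ 18) for a Poisson mean of 30 is 0.993, against the plan's 0.99.
- Enrolment: 60 / 0.90 = 66.7, rounded up to 67.

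The chain allows 10% for drop-out and nothing for participants lost to a missing covariate.

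**3. If participants were lost**

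The documents give no missing rate, so the share *s* of the 60 evaluable participants who lack at least one baseline-only covariate is an assumption. I also assume that those lost have the same event rate as the rest. Then:

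- expected events = 30 × (1 − *s*);
- chance of at least 18 = Poisson tail at that mean;
- enrolment that keeps 60 complete participants = 60 / (1 − *s*) / 0.90, rounded up.

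| *s* | Expected events | P(at least 18) | Enrolment |
|---|---|---|---|
| 0% | 30.0 | 0.993 | 67 |
| 2% | 29.4 | 0.990 | 69 |
| 5% | 28.5 | 0.986 | 71 |
| 10% | 27.0 | 0.973 | 75 |
| 15% | 25.5 | 0.950 | 79 |
| 20% | 24.0 | 0.913 | 84 |
| 30% | 21.0 | 0.773 | 96 |

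**4. What a large loss would require**

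With *k* covariates, each missing independently in a share *m* of participants, *s* = 1 − (1 − *m*)^*k*.

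- *k* = 10, *m* = 1%: *s* = 9.6%, 27.1 events, P = 0.974.
- *k* = 10, *m* = 2%: *s* = 18.3%, 24.5 events, P = 0.928.
- *k* = 8, *m* = 5%: *s* = 33.7%, 19.9 events, P = 0.696.
- *k* = 10, *m* = 5%: *s* = 40.1%, 18.0 events, P = 0.528.

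The severe results need many covariates with unrelated gaps. If gaps cluster in the same people, fewer participants are affected at the same item rates.

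**5. If imputation or an unknown category is allowed for model building**, no participant is lost on this account: the expected number stays at 30 and the probability at 0.993.

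**The case against.** A reader might infer that the plan deletes every day and event of any participant who lacks one covariate. The documents do not say that. No section excludes such a participant from any model. SAP 3.4.5.2 states that "feature extraction and selection algorithms will be used", SAP 3.4.2 speaks of features being considered and not of all being kept, and other methods and packages are allowed. Dropping the covariate, or coding the gap as unknown, would keep every event without replacing a value. This stands: deletion is one possible consequence, not a stated rule. But feature selection is planned to improve performance, not to handle missing data, and the plan does not choose between these routes.

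The across-instance sentence may be read as already permitting imputation. That reading is open, but it contradicts the opening sentence of the same section.

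Gaps may also be few. Age and COPD stage are needed for eligibility and should be nearly complete. Protocol Table 4 schedules the main baseline items at Day 0, and protocol 9.6.3 provides queries for incomplete entries. This stands too, and is why the lower part of the range is the more plausible. The 36-month exacerbation count is the one model covariate singled out as possibly unavailable.

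SAP 3.4.6 adds that "sensitivity analyses will be performed to run models with variables with a missing rate less than or equal to 20" per cent. That limits variables, not participants, and a covariate missing in 10% of participants passes the cut-off with its gaps intact.

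Finally, protocol 9.10.3 reviews exacerbation frequency every 2 weeks against the minimum of 18, and the study is declared exploratory. Both lower the stakes. However, that review counts observed exacerbations, not those usable in a given model.

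**Conclusion.** The point holds as an inconsistency in the missing-data rules with a conditional consequence. The baseline-only rule is unqualified, it covers inputs to the primary prediction model, and it lacks the machine learning exception given to the other classes. The across-instance sentence does not settle the matter. Models needing complete rows are left to drop the covariate or the participant, and the algorithms may be scored on different people.

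The size is unknown, because no missing rate is given. With 5% to 20% of participants lost, the chance of at least 18 events falls from 0.993 to between 0.986 and 0.913, and expected events stay at 24 or more. This rests on the plan's rate of 0.5 events per participant and on loss unrelated to event risk. Figures near 0.5 arise only if about ten covariates each have independent gaps of 5%, which nothing in the documents suggests. This is a worthwhile and inexpensive improvement, not a threat to the study's feasibility.

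**What to change.** In SAP 3.4.4, and in protocol 9.7.1.2 when it is next amended:

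- Limit the no-replacement rule for baseline-only variables to descriptive analyses, and state whether the across-instance sentence applies to them.
- For Objectives 2 and 5, impute baseline-only covariates by median or mode with a missing indicator (or an unknown category for categorical items), or by iterative imputation. Fit the imputation inside each training fold, so that nothing from the held-out data enters it.
- Evaluate all algorithms on the same rows. Report the missing rate of each covariate, and any participants and events lost per model.

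The cost is a paragraph of SAP text and a few lines of code. The downside is reliance on a simple imputation for a few covariates; the sensitivity analyses on imputation already planned in SAP 3.4.4 can be extended to cover it.

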### 3.4.5 Analysis of outcomes

#### 3.4.5.1 Primary Objective 1

Descriptive statistics will be reported in terms of mean (SD) or median (IQR) for continuous variables, as well as counts and frequency (%) for categorical variables of sensor collected data described in section 2.1.4, comprised of

- physical activity,
- heart rate,
- resting heart rate,
- heart rate variability (10 variables),
- temperature,
- respiration rate,
- ratio of in- vs. expiration time
- cough frequency,
- sleep pattern (hours of sleep),
- frequency of additional medication

measured for each patient

1. at baseline (Day 0),
2. in the period Day 8 to Day 14 (intra-individual period average),
3. from 14 days prior to an exacerbation onset, in a 7-day sliding time window, in a 3-days sliding time window, and a 1-day sliding time window,
4. at the onset of an exacerbation (first day of exacerbation period),
5. from the end of an exacerbation to 14 days after, in a 7-day sliding time window, in a 3-days sliding time window, and a 1-day sliding time window,
6. 14, 21, and 28 days after an exacerbation.

The analysis will be repeated for different exacerbation severities:

1. Exacerbations of any (moderate or severe) severity are counted
2. Only severe exacerbations are counted
3. Only moderate exacerbations are counted
4. Only mild exacerbations are counted

Results will be reported in one table per parameter, with descriptive statistics indexing rows and measurement times indexing columns.

For each continuous parameter, mean values will be plotted across all daily measurement time points during the 3-month observation period, together with 95% CIs based on the normal approximation (t-statistic).

### 3.4.5.2 Primary Objective 2

To predict moderate or severe COPD exacerbations by building a statistical model employing sensor-derived data and demographic and medical covariates.

To generate several features needed as input to the model a number of algorithms (e.g., self-learning algorithms) for obtaining derived parameters such as cough frequency, physical activities and sleep pattern will be developed first using the label dataset obtained via the app (see Section 3.4.3).

Different machine learning algorithms will be evaluated, and their performance will be assessed by estimating their accuracy, specificity, sensitivity, and area under ROC metrics. Other usual evaluation metrics such as precision, positive predictive value (PPV), negative predictive value (NPV), F1-score will be computed.

This analysis will be performed on the COPD cohort. Internal cross-validation will be tested.

The following models will be used:

- Logistic regression
- Random Forest
- K-nearest neighbors
- Boosting methods (e.g., Gradient boosting machine, GBM)
- Support vector machines (SVM)

Other methods may be tested.

The development of those models will be based on the machine learning algorithms implementation of scikit-learn (12), a python package designed for predictive data analysis. Other packages may be considered if needed (e.g., H2O (13)).

To optimize the performance of the models, feature extraction and selection algorithms will be used.

Explanatory models will be built on top of the selected machine learning algorithm (14), as a way to support rationalization for physicians and regulatory organizations. Depending on the selected ML model selected, either model specific (for logistic regression, decision trees, k-nearest neighbors) or model agnostic methods will be considered (global methods as PDP, ALE, functional decomposition, and local methods as LIME and Shapley values).

### 3.4.5.3 Secondary Objective 3

Objective 3 will be analyzed on the COPD cohort. For each pair of variables and outcomes ( $x, y$ ) defined below, Pearson's correlation coefficient will be computed together with a 95% asymptotic confidence interval based on Fisher's Z transform.

In case of low variability in parameter values (e.g., exacerbation count), parameters may be treated as ordinal and analyzed in terms of Kendall's Tau statistic with non-parametric confidence interval (see (15)).

The following variable groups and outcomes will be paired and assessed at the indicated time points:

Group x	Group y	Time points for assessment
Sensor data (see section 2.1.4), daily averages (17 variables): physical activity, heart rate, resting heart rate, heart rate variability, temperature, respiration rate, ratio of in- vs expiration time, cough frequency, sleep pattern (hours of sleep)	CAT summary score: Self-assessed patient's health status by CAT questionnaire.	Baseline (Day 0), End of study visit
	Lung function parameters by plethysmography (see section 2.1.3, 13 parameters)	Baseline (Day 0), End of study visit
	Laboratory values (see section 2.1.3, 20 parameters): Current or last available (capillary) pO 2 , O 2 saturation and pCO 2 ; Serum CRP and serum procalcitonin levels; blood count (CBC with differential)	Baseline (Day 0), End of study visit
	Exacerbation count by mild, moderate or severe exacerbation.	End of study visit

For each pair of groups (x, y) and for each assessment time point, a table with x and y parameter groups indexing rows and columns respectively, will be provided to display coefficient of correlation and 95% CI for all parameter pairs. To provide a visualization, the tables will be plotted as matrix heatmaps displaying the correlation coefficient point estimates.

#### 3.4.5.4 Secondary Objective 4

Sensor derived data may be related to the CAT score, therefore, an additional objective is to investigate whether changes in physical activity, heart rate, heart rate variability, temperature, respiration rate, cough frequency, and sleep pattern in the 3-month observation period, are associated with changes of the patient self-assessed symptoms (CAT).

This analysis will be performed on the COPD participants set.

The following analyses will be conducted in this order:

- Linear mixed model with the patient self-assessed symptoms, CAT score, mean value assessed on a 7-day basis as the response variable and the mean values of physical activity, heart rate,

heart rate variability, temperature, respiration rate, cough frequency also assessed in the same timeframe as the independent variables. Individual trajectories will be investigated. A model including the change of each sensor variable, the time (7-day period) as fixed effect will be tested. Interaction terms between the time and each sensor variable will be included in the model and potentially patient-level random intercepts and slopes will also be included in the model. Other covariates such as age, sex, smoking status, medical history will be considered. The same model will be considered with the absolute change of the CAT score and the absolute change of the sensor variables.

$$Y_{ij} = (\alpha + a_i) + (\beta + b_i) X_{ij} + \xi_{ij}$$

where  $a_i$  is the random intercept,  $b_i$  is the random slope for the  $j^{\text{th}}$  observation of the individual  $i$

- The analysis above will be repeated on the COPD participants with severe/moderate exacerbations in the time-window considering the 14 days prior the exacerbations. Daily values of the CAT score and of the physical activity, heart rate, heart rate variability, temperature, respiration rate, cough frequency, and sleep pattern will be considered in the model.

The relation between the change of the patient self-assessed symptoms (CAT score) and the changes of the physical activity, heart rate, heart rate variability, temperature, respiration rate, cough frequency, and sleep pattern during the 3-month observation period will be further evaluated using linear spline regression to infer the location of the changepoints.

[figure not shown]
#### 3.4.5.5 Secondary Objective 5

To predict the CAT score and changes thereof by building a statistical model employing sensor-derived data and demographic and medical covariates

[figure not shown]
This analysis will be performed on the COPD participants set.

Similar to Primary Objective 2, different machine learning algorithms will be evaluated, and their performance will be assessed by estimating their accuracy, specificity, sensitivity, and area under ROC metrics. Other usual evaluation metrics such as precision, positive predictive value (PPV), negative predictive value (NPV), F1-score will be computed.

[figure not shown]
CCI

CCI

CCI

CCI

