9.5 Study Size

Sample size calculation is based on the second part of the primary objective, especially on predicting exacerbations of a severe or moderate type as outcome.

Assuming a desirable sensitivity and specificity of 0.85 for our algorithm and requiring that the lower 95% confidence limit should be at least 0.50 (with a probability of 0.95) for this exploratory approach, the number of observed exacerbation events needed is 18 ([Flahault 2005](#)).

Assuming that patients with COPD within our eligibility criteria (GOLD stage II-IV with a history of at least 2 moderate and/or severe exacerbations within any 12 month period within the last 3 years and at least 1 moderate or severe exacerbation within the last 12 months) show a frequency of 2 moderate or severe exacerbations per year, participants with COPD will have 0.5 events in 3 months (the in-study time). Further assuming that event occurrence over 3 months for every individual participant follows a Poisson distribution with parameter $\lambda = 0.5$, the number of events in the overall study population is also Poisson distributed and the corresponding parameter is the sum of individual parameters λ . Calculations show that a λ of 30 is needed to reach an upper cumulative distribution probability of 0.99 for observing at least 18 exacerbations. Therefore, 60 participants are needed to observe at least 18 exacerbation events within the 3-month observation period.

The events of interest in the context of the present study are COPD exacerbations (severe or moderate), exactly the onset of an exacerbation. For building the binary classifier predictive models we also require “no exacerbation” events. We will sample such events randomly from periods with no exacerbations, avoiding 2 weeks before and after an exacerbation.

Considering a drop-out rate of 10%, the estimated number is 67 participants with COPD that need to be included in this study.

This recruitment number is also in good agreement with published studies with regards to the ability to build predictive models for exacerbations. Studies with similar recruitment numbers ([Yañez 2012](#)) have been able to predict exacerbations based on single parameters studied. Strong features can compensate for low numbers in COPD machine learning model building as shown in

[Al Rajeh 2020](#), and using several features improves the accuracy of predictive models as seen in [Jensen 2012](#).

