9.7.2.1 Primary Objectives

Primary objective 1): To describe the distribution of sensor collected data on physical activity, heart rate, heart rate variability, temperature, respiration rate, cough frequency, and sleep pattern, by severity of COPD exacerbations.

This analysis will be performed on the COPD participants set.

- Sensor collected data on physical activity, heart rate, heart rate variability, temperature, respiration rate, cough frequency, sleep pattern, at baseline (Day 0), in the period Day 8 to Day 14, and shortly prior (14 days prior to, 7 days prior) to, during an exacerbation and after an exacerbation (8 to 14 days after, 2 weeks after, 3 weeks after, up to 4 weeks after an exacerbation) will be reported as mean (SD) and/or median (Interquartile Range) for continuous variables and counts and frequency (%) for categorical variables. The analysis will be done on the group of severe or moderate exacerbations and on exacerbations by type.

Primary objective 2): To predict moderate or severe COPD exacerbations by building a statistical model employing sensor-derived data and demographic and medical covariates.

This objective aims at predicting the occurrence of a severe or moderate exacerbation, in other words, predicting an event out of the combined group of severe and moderate exacerbations. It is desirable to predict an AECOPD as early as possible, therefore dependency of model metrics on the time period before exacerbation will be explored.

As input to the model a number of algorithms (e.g. self-learning algorithms) for obtaining derived parameters such as cough frequency, physical activities and sleep pattern, heart rate variability, temperature, respiration pattern, cough frequency, or sleep pattern will be developed first using the labeling of activities dataset obtained via the app. Said derived features will help to understand the importance of different raw data patterns, so that explanatory models can be built on top of the machine learning algorithms (Molnar 2022), as a way to support rationalization for physicians and regulatory organizations.

Different machine learning algorithms (e.g. gradient boosting, SVMs, K-nn) will be evaluated, and their performance will be assessed by estimating their accuracy, specificity, sensitivity, and area under ROC metrics.

This analysis will be performed on the COPD participants set.

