9.9 Limitations of the Research Methods

- The data is collected from a very limited number of study sites in Germany. Hence the study population may not be representative of the population of patients with COPD. In addition, the fact that participation in the study requires cognitive capabilities to use applications and devices used for data collection in the study may cause selection bias towards a younger age group.
- Daily averages will be calculated to represent continuous measurements each day. There may be additional information encoded in smaller time periods (hour by hour or minute by minute) data or through defining bouts of activity.
- Some of the outcomes are based on subjective self-assessment e.g. COPD symptoms and health status will be assessed by the CAT score. In validation studies, the CAT score has been shown to be a valid and reliable tool to assess perceived health status (Jones 2013), though validity of the online version remains to be proven.
- The number of observed exacerbations will be low, and predictive models will need to be refined and validated in a larger population.

- Severe and moderate AECOPDs will likely be encountered in only ~40% of the participants with COPD. This may impact the generalizability of predictive models for AECOPDs.
- This study is a national study in Germany and will only recruit patients with sufficient proficiency in the German language. It is therefore impossible to assess potential bias in the gathered data and conclusions with regards to language, ethnicity, cultural background, country of origin, and social factors not encountered in the study population. This refers both to PROs and the interpretation of sensor data. Future studies will need to study these potential biases in a multinational setting.
- Mild exacerbations are captured via the labelling section in the patient facing application as “additional medication used” (self-reporting). Therefore, the capture of mild exacerbations depends on patients’ adherence to the intended application use and daily reporting. Mild exacerbations may therefore be under-reported (but also over-reported in case of erroneous entries).
- Participants may not adhere to the intended constant wearing or charging regimens of the device and therefore available data may have too many gaps to allow meaningful interpretation.

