### 3.2 ANALYSIS SETS

The study will have two main analysis sets:

- COPD cohort: all patients with COPD fulfilling all of the inclusion criteria and none of the exclusion criteria (see Section 1.3.1);
- Calibration cohort: participants in the calibration cohort as defined in Section 1.3.1

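### In the Objective 1 tables, the baseline columns are not limited to participants who exacerbate, so comparing them with an exacerbation window mixes who contributes with change around the event

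*SAP*

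**What the plan says.** SAP 3.4.5.1 reports mean (SD) or median (IQR) of each sensor parameter, "measured for each patient", at six kinds of time point. Two are baselines: Day 0, and each participant's average over Day 8 to 14. The other four are tied to an exacerbation: sliding windows in the 14 days before onset, the first day of the exacerbation, sliding windows in the 14 days after its end, and days 14, 21 and 28 afterwards. All of them become columns of the same table: "Results will be reported in one table per parameter, with descriptive statistics indexing rows and measurement times indexing columns". The tables are repeated for moderate or severe, severe only, moderate only and mild exacerbations.

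Protocol 9.7.2.1 says of Objective 1: "This analysis will be performed on the COPD participants set". SAP 3.2 defines that set without reference to having an event: "COPD cohort: all patients with COPD fulfilling all of the inclusion criteria and none of the exclusion criteria". Protocol 9.9 expects that "Severe and moderate AECOPDs will likely be encountered in only ~40% of the participants with COPD".

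Protocol 9.3 makes Day 8 to 14 the sensor baseline, gives measuring parameter changes as one of its uses, and moves it to another period if an exacerbation is close. SAP 3.4.5.1 uses fixed Day 8 to 14, does not apply the moving rule, and plans no change from baseline. SAP 3.4.3 says that sensor temperature is meaningful only as a relative value for assessing changes, yet temperature is one of the parameters summarised here as a level.

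**The concern.** A reader of these tables will look from the baseline column to the onset column and take the difference as what happens around an exacerbation. The two columns do not contain the same people. If participants who go on to exacerbate already differ at baseline, for example by moving less or coughing more, the columns differ even when nothing changes around the event. A difference in the opposite direction could mask a real change. Protocol section 7 makes a baseline difference plausible: it says that CAT scores are higher in people with more frequent exacerbations and that CAT closely reflects functional status.

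The data are paired, since each participant with an event is followed from Day 0, but no Objective 1 output uses the pairing. A reader cannot recover the within-participant change, or its precision, from column means and SDs.

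**Working it through.** **Share who contribute to the exacerbation columns.** Protocol 9.5 assumes 2 moderate or severe exacerbations per year, so a Poisson mean of 0.5 per participant over 3 months, and 60 participants after drop-out (67 enrolled).

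- P(at least one event) = 1 − exp(−0.5) = 39.3%, which reproduces the protocol's figure of about 40%.
- 60 × 0.393 = 23.6, so about 24 of 60 (67 × 0.393 = 26.4 of 67). About 61% of those who can enter the baseline columns cannot enter the exacerbation columns.
- P(two or more events) = 1 − 1.5 × exp(−0.5) = 9.0%. The SAP does not say whether these participants enter a window once or once per event.

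**Column difference when nothing changes.** Let f be the share who exacerbate and d their baseline difference, in SD, from those who do not. Take the mean of those who do not as 0. The baseline mean over everyone is f·d and the window mean is d, so the columns differ by (1 − f)·d. With f = 0.4 and d assumed, because the documents do not give it:

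| d (SD) | Column difference (SD) |
|---|---|
| 0 | 0 |
| 0.2 | 0.6 × 0.2 = 0.12 |
| 0.5 | 0.6 × 0.5 = 0.30 |
| 0.8 | 0.6 × 0.8 = 0.48 |

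A simulation with 60 participants, d = 0.5 and no true change gave a mean column difference of 0.31 SD and a mean paired change of 0.00 SD.

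**Severe events alone.** The documents give no share of events that are severe. If 10% to 30% of events are severe, f = 1 − exp(−0.05) = 0.049 to 1 − exp(−0.15) = 0.139, or about 3 to 8 of 60 participants. At d = 0.5 the column difference is then 0.48 to 0.43 SD, close to d itself.

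**Precision.** Assume SD 1 at each time point, one event per exacerbating participant, and within-participant correlation ICC (also assumed). The 24 are among the 60, so the two column means have covariance ICC/60.

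- SE of the column difference = √(1/60 + 1/24 − 2·ICC/60)
- SE of the paired change = √(2(1 − ICC)/24)

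| ICC | Column difference (SD) | Paired change (SD) |
|---|---|---|
| 0.7 | 0.19 | 0.16 |
| 0.8 | 0.18 | 0.13 |
| 0.9 | 0.17 | 0.09 |

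At ICC 0.5 both formulas give √(1/24) = 0.20, so the gain in precision depends on a correlation above 0.5. Removal of the composition shift does not.

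**Whether another output supplies the contrast.** The Objective 1 plots show cohort means by study day, not aligned to onset. Objective 4 (SAP 3.4.5.4) includes changes in sensor variables and the 14 days before moderate or severe exacerbations, but its response is the CAT score. Neither gives sensor change from own baseline to an exacerbation window.

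**The case against.** The strongest reply is that Objective 1 only asks for a description of distributions by exacerbation severity. No contrast between columns is planned, the study is expressly exploratory, and prediction belongs to Objective 2. SAP 3.4.1 reports numbers of observations and missing values, so unequal denominators will be visible. This stands in part: nothing inferential fails. But seeing 60 beside 24 does not let a reader correct for who is absent.

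A reader might infer that the whole table is confounded. The layout does not support that. Only Day 0 and Day 8 to 14 can include participants without an event. The course from 14 days before onset through recovery is read in largely the same people, apart from missing or truncated days.

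A reader might also compute the standard error of the column difference as √(1/60 + 1/24) = 0.24 SD and set it against the paired values. That treats the columns as independent groups, which they are not. The values allowing for the shared participants are 0.17 to 0.19 SD, so pairing gains less than that comparison suggests.

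Finally, d may be small. Every COPD participant is selected for prior exacerbations, and the sample-size model gives all of them the same event rate. Neither rules out a baseline difference, but neither establishes one.

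**Conclusion.** The point holds for comparisons between an exacerbation window and either baseline column. With no true change, such a comparison is off by about 0.6d in the moderate or severe table and by nearly d in a severe-only table. The size and direction rest on d, which the documents do not give; 0.5 SD is an illustration, not a finding. The 40% share applies to moderate or severe events only, and no share is given for mild ones.

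The paired change removes this composition shift and, at an assumed ICC of 0.7 to 0.9, is also more precise. The documents do not support the conclusion that an analysis is invalid, since this is a descriptive objective with no planned test. One reservation remains: only the heading of the TLF plan (SAP Appendix 1) was available, and the wording on measurement for each patient covers all six time points, so a table shell could still restrict the baseline columns. The SAP body does not.

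**What to change.** In each severity table of SAP 3.4.5.1:

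- Show the baseline column for the participants who contribute to that table's exacerbation windows. A whole-cohort baseline can stay as a separate, labelled column.
- Add the within-participant change from own stable baseline to each window, with mean, SD and 95% CI clustered on participant, using the baseline rule in Protocol 9.3.
- Give the number of participants and the number of events in every column, and state how repeat events enter.

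The cost is a few extra columns and no new data. SAP 3.1 plans a single analysis after the last participant has finished, so this can be specified beforehand. The severe-only table will rest on small numbers, and its intervals should be read accordingly.
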